Clinical Trial Protocol

Physiologic Phacofluidics: Ghost Protocol

Protocol Number: 83557125

Principal Investigator: [name] PHD
Address Wolfe Eye Clinic
[name]
[name]

[contact]

IRB: Advarra

This protocol is confidential and the information available within it may not be reproduced or otherwise disseminated.

Physiologic Phacofluidics: Ghost Protocol

Protocol V4.0

Date: 9/30/2023

Purpose: To investigate the early post-operative clinical benefits when performing phacoemulsification at physiological intraocular pressure (IOP) using Centurion® Vision System with Active Sentry® handpiece

Background: Phacoemulsification and intracapsular lens implantation is the most common performed eye surgery to correct vision loss and restore vision for patients with cataract. During phacoemulsification, the ocular environment changes because of the heat generated by dissipated ultrasound energy, high perfusion, fluctuation in intraocular pressure (IOP), and the inflammatory response resulting from surgical manipulation.

Historically, the advances of phacoemulsification cataract surgery technologies have been geared towards increased efficiency of cataract removal, decreasing intra-operative complications, and faster post-operative visual recovery. A long-standing dogma of phacofluidics has been that high non-physiologic IOP settings (>65 mm Hg) are required for highly efficient cataract extraction. However, studies are showing that operating at lower IOPs levels are as safe and efficacious¹; and "physiological phaco" between 20-30mmHg may yield additional intra-operative and post-operative benefits:

- The lack of significant and rapid pressurization changes will result in significantly less early corneal edema in after cataract surgery²
- The normotensive intra-operative environment is gentler on the corneal endothelium resulting in clearer and healthier corneas in the short and long term; Some suggest that an increase in central corneal thickness (CCT) on the first postoperative day correlates with surgical trauma to the endothelium and that it is proportional to cell loss at 3 months³
- The Active Sentry (AS) Handpiece can maintain anterior chamber stability at low IOP settings, thus providing added safety and a gentler intra-operative environment^{1,4}
- Elicit a lower post-operative inflammatory response²

Several studies have looked at inflammatory indicators in FLACS (femtosecond laser-assisted cataract surgery)^{8,9}.

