There has been minimal research on the clinical benefits in early post-op (initial hours after surgery) care and no studies evaluating inflammatory response in early post-operative stages with cataract surgery performed at near physiological IOP.

As cataract surgeons ever strive towards matching the speed of recovery and accuracy of visual outcomes of our corneal refractive counterparts, near physiologic phacoemulsification with the safety of the Centurion Active Sentry handpiece combined with low IOP phacoemulsification settings will likely be a key technological step forward towards that goal.

Methods:

Study population

Inclusion Criteria

- Patients without prior ocular surgery both eyes
- Adult patients with visually significant cataract with WHO-World Health Organization NUC grade 2-3
- First eye only undergoing uncomplicated cataract surgery
- Unremarkable systemic history; controlled diabetes with HbA1c <7%
- Unremarkable ocular health
- Anterior chamber depth ACD >2.04mm¹⁰
- Age range 55-95

Exclusion Criteria:

- Prior ocular surgery including corneal refractive surgery, cataract surgery in fellow eye
- Thin corneas (<490 microns)
- Complicated (use of pupil expansion devices) or prolonged cataract surgeries (>15 mins) with post-operative complications (IOP spike >30mmHg), severe punctate keratitis

Approximately 66 patients will be identified and included in the study. Patients at the day of surgery sign up will be randomized to high (65mmHg) vs low IOP (20mmHg) using a random online number generator; Even will be high IOP; Odd will be low IOP. Patients will undergo standard cataract surgery with equivalent vacuum and aspiration rates in both groups for the duration of the entire cataract surgery; IOP settings will be set at high vs low IOP but may be adjusted if necessary for the safety of the patient.

In all procedures, the intraocular lens (IOL) implanted and the ophthalmic viscosurgical device (OVD) materials used will be standardized to the same materials and are part of routine surgery. Cumulative dissipated energy (CDE) and surgical duration will be collected for all patients. An intraoperative aqueous sample 100-150µL will be collected at the end of the case 2 minutes after OVD removal and immediately transferred on dry ice to a laboratory, stored at -80°C until analysis as established in prior protocol.⁶ The extraction of aqueous sample will not require additional incisions.

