Any adverse events (AE) will be recorded in subject's medical charts as well as an adverse event log. AEs are classified as serious or non-serious; expected or unexpected; and study-related, possibly study-related, or not study-related. Serious AEs will be reported immediately to the regulatory authorities as per standard of care. The potential risks involved are that of standard cataract surgery with potential complications and side effects associated with any surgical procedure. These include but are not limited to: infection, macular edema, increased IOP, general risk of anesthesia and surgery, bleeding in the eye, and decreased vision. Some potential benefits include: improved visual acuity, decreased glare symptoms, lowered IOP, and faster visual recovery.

Analysis:

Primary endpoint: Difference in mean CCT change at 4 hrs post-surgery between high vs low IOP will be assessed using t-test with a P-value <0.05. Descriptive statistics will be used for the other secondary endpoints

Sample Size Justification:

In Vasavada et al²., the expected mean CCT change between the high vs low groups is hypothesized to be 32um, with a standard deviation of 40um. With a Type I/II error rate of alpha=0.05 and power=0.85, a sample size of 56 eyes are needed; additional 10 eyes to account for ~15 attrition; N=66

Data Collection and Management:

Data is recorded in a manner that reduces the risk of a breach of confidentiality. Password protected Microsoft Excel files will be utilized for this study and only accessible by authorized study personnel.

Ethical and Regulatory Considerations:

The study is conducted in accordance with the following:

Protocol and study-related plans and documents

- Local regulations, as applicable
- Good Clinical Practices, as outlined in the ICH Harmonized Tripartite Guideline for GCP (ICH)

E6(R2))Ethical and Regulatory Considerations:

The study is conducted in accordance with the following:

- Protocol and study-related plans and documents
- Local regulations, as applicable
- Good Clinical Practices, as outlined in the ICH Harmonized Tripartite Guideline for CP (ICH)
- The ethical principles established by the Declaration of Helsinki
- Regional participant data protection laws and regulations
- Local IRB requirements

Institutional Review Board (IRB):

The study site will maintain an accurate and complete record of all reports, documents and other submissions made to the Institutional Review Board (IRB) concerning this protocol.

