The investigator must supply ongoing study progress reports to the IRB, per local requirements, protocol deviations and amendments. In addition, the investigator must notify the IRB at the closure of the study.

Informed Consent:

It is the responsibility of the investigator and clinical coordinator to inform each subject of the purpose of this study, including possible risks and benefits and document the informed consent process in the subject's chart. Prior to entry into the study or initiation of any study-related testing, the subject must read, sign and date the informed consent form. If the subject's vision is impaired to the point where they cannot read the informed consent document, the document will be read to the subject. The person executing the consent must also sign and date the consent form. One original informed consent form is to be retained by the study site and a copy is to be given to the subject.

Protocol Amendments:

This protocol must be followed as written. Any change or addition to this protocol that impacts subject safety, or the validity of the study requires a written protocol

amendment that must be approved in writing by the IRB and any required regulatory authorities before implementation.

Record Keeping and Retention:

Data generated for the study should be stored in a limited-access file area and be accessible only to study personnel of the site. All reports and communications relating to study participants will identify participants only by subject identification number. Complete subject identification will be kept by the investigator. This information will be treated with strict adherence to professional standards of confidentiality.

The Investigator will retain a copy in the study file:

- A copy of the IRB approved informed consent form
- All original informed consent forms with required signatures
- All participant source documents, etc.
- All IRB correspondence (i.e., informed consent [including any approved revisions], protocol, AE, advertisements, newsletters).

Confidentiality:

All clinical study findings and documents are regarded as confidential. Study documents (protocols and other material) must be stored appropriately to ensure their confidentiality.

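### Does the allowance to adjust the IOP setting during surgery leave the primary comparison undefined?

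*Combined protocol and SAP*

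**What the plan says.** The Methods section randomises each eye on the day of surgery to 65 mmHg or 20 mmHg, keeps vacuum and aspiration equivalent between the groups, and then states that "IOP settings will be set at high vs low IOP but may be adjusted if necessary for the safety of the patient". No trigger, size or direction of adjustment is given.

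On intra-operative data, Methods states that "Cumulative dissipated energy (CDE) and surgical duration will be collected for all patients", and an aqueous sample is taken. The IOP setting used is not named there.

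The Analysis section gives the primary analysis in one sentence: "Difference in mean CCT change at 4 hrs post-surgery between high vs low IOP will be assessed using t-test". It names no analysis set. The paragraph that defines the endpoints, after the visit table, places the primary contrast between the high and low IOP groups.

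The Exclusion Criteria include some events known only at or after surgery, among them "prolonged cataract surgeries (>15 mins) with post-operative complications". A changed IOP setting is not one of them.

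The Institutional Review Board section mentions deviations only as a reporting matter ("per local requirements, protocol deviations and amendments"). Record Keeping and Retention requires the investigator to keep "All participant source documents, etc".

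**The concern.** The IOP setting is the only randomised factor, and the surgeon may change it. Eyes changed for safety are unlikely to be a random subset. Three treatments of such an eye are conceivable: leave it in its randomised group, move it to the group nearer the setting used, or leave it out. No sentence rules out the last two.

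Some wording seems to invite them. The Purpose is framed by the pressure at which surgery is performed, and the exclusions already contemplate removing eyes after allocation. If adjusted eyes were moved or dropped, the comparison would no longer be the randomised one and could show a CCT difference when the settings have no effect. If the choice were made after the CCT results were seen, one dataset could give different primary results. Because the setting is not listed as study data, a reader might also be unable to learn how many eyes departed from their allocation.

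**Working it through.** **1. The plan's own figure.** Sample Size Justification states that "the expected mean CCT change between the high vs low groups is hypothesized to be 32um, with a standard deviation of 40um", with alpha 0.05 and power 0.85. Taking the test as two-sided with 1:1 allocation, n per arm = 2 × (1.960 + 1.036)² × (40/32)² ≈ 28.06, or 56 eyes in total, as stated. For attrition of about 15%, 56/0.85 = 65.9, which gives 66. The checks below use 28 and 33 eyes per arm.

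**2. Which groups exist.**
- Methods forms two groups, both by randomisation.
- The endpoint paragraph compares the high and low groups.
- Analysis tests high against low.
- No section forms a group by the setting used, and no exclusion lets an eye be dropped because its setting changed.

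Read together, these sections point to analysis as randomised.

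**3. What each handling does when there is no true effect.** The documents give no adjustment rate, so these inputs are assumptions. A share p of eyes in both arms is difficult, with mean CCT change higher by d. Only the low arm's difficult eyes are adjusted. Total SD is 40 um.
- As randomised: both arms have mean p·d, so the bias is 0.
- Dropped: high mean p·d, low mean 0, so the bias is p·d.
- Moved to high: high mean (p·d + p·d)/(1 + p), low mean 0, so the bias is 2pd/(1 + p).

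For p = 0.10 and d = 20, the bias is 0.10 × 20 = 2.0 um if dropped and 2 × 0.10 × 20/1.10 = 3.6 um if moved. False-positive rates come from simulation (200,000 trials per cell, pooled two-sided t-test at 0.05):

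| p, d | Bias dropped / moved (um) | Rate dropped, 28 / 33 per arm | Rate moved, 28 / 33 per arm |
|---|---|---|---|
| 10%, 20 | 2.0 / 3.6 | 5.4% / 5.4% | 6.2% / 6.3% |
| 10%, 40 | 4.0 / 7.3 | 6.4% / 6.7% | 9.6% / 10.7% |
| 20%, 20 | 4.0 / 6.7 | 6.4% / 6.5% | 9.0% / 9.8% |
| 20%, 40 | 8.0 / 13.3 | 10.7% / 11.8% | 21.6% / 25.0% |

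As randomised, the rate is 4.9% to 5.1% in every cell. At p = 5% and d = 20, dropping or moving leaves the rate within about 0.3 percentage points of 5%. If adjustment is equal in both arms, or adjusted eyes do not differ (d = 0), there is no bias. If only high-arm eyes are adjusted, the bias reverses. Taking SD 40 within difficult and ordinary eyes, instead of overall, lowers the largest rates at 28 per arm to 9.8% (dropped) and 18.8% (moved).

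**4. Power as randomised.** If adjustment moves an eye towards the other arm's setting, the expected difference is 32 × (1 − share adjusted in one arm × fraction of effect lost). Power is from the noncentral t distribution with SD 40:

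| Eyes adjusted in one arm | Difference (um) | Power, 28 / 33 per arm |
|---|---|---|
| None | 32.0 | 84% / 89% |
| 10%, half the effect lost | 30.4 | 80% / 86% |
| 20% half lost, or 10% all lost | 28.8 | 75% / 82% |
| 20%, all lost | 25.6 | 65% / 73% |

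This loss comes from the adjustments themselves. Writing down an analysis set would not recover it.

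**The case for a change.** The best case for a change is that the plan never states analysis as randomised, no separate SAP settles it, and a sentence plus one data item would cost almost nothing. An analyst could move or drop an adjusted eye without contradicting any sentence, and without the settings recorded the trial could not report adherence to allocation.

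The silence stands, and so does the arithmetic. The rest is weaker than it looks. The Purpose describes the intervention, not an analysis set. The surgery-related exclusions do not extend to an adjusted setting; whether they should remove randomised eyes at all is a separate question. Protocol Amendments requires the protocol to be followed as written, and Publication calls for review of the complete data. Both are general statements, but they lean against reassigning eyes.

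The largest figures also need an unlikely combination: a fifth of one arm adjusted, none of the other, a full standard deviation of extra swelling, and a changed low setting counted as belonging to the 65 mmHg group. The Background puts physiological surgery at 20 to 30 mmHg, so a modest rise from 20 would not place an eye in the high group.

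Nor is it certain that keeping adjusted eyes as randomised dilutes the contrast, since no direction of adjustment is given. The false-positive rate with no true effect does not depend on direction.

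A record of the setting used would be useful for describing adherence, and retained operative records may hold it, though the protocol does not say so. It would not alter the primary result.

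**Conclusion.** The gap is one of wording, which an analyst fills sensibly by analysing eyes as randomised. That is the natural reading of Methods, the endpoint paragraph and Analysis together. It carries no bias and a 5% false-positive rate when the settings have no effect. No stated rule produces a wrong result, and the sample size of 56, raised to 66, reproduces.

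The possible harm depends on an analyst departing from that reading. Under modest assumptions (10% of one arm adjusted, 20 um more swelling) it is 0.4 percentage points of false-positive rate if eyes are dropped, and 1.2 to 1.3 points if they are moved. Larger values need more extreme assumptions, and the documents support none of these rates. No change to the plan is needed on this point.

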All subjects will be prescribed the standard post-operative cataract surgery medications (not specific to study). Post-operative visits by the masked sub-investigator will perform the following procedures at 4hrs (early post-op), POD#1 (20-24hrs), POW#1:

Post-op Procedures	Baseline	Visit1 (4hrs)	Visit2 (20-24hrs)	Visit3 (1 week)
Pachymetry	X	X	X	X
Visual acuity	BCVA	UCVA/PHVA	UCVA/PHVA	UCVA/PHVA
Slit Lamp- Cell /Flare	X	X	X	X

Pachymetry: a painless, simple test where a probe is gently placed on the front of the eye to measure the thickness of the cornea.

Best-corrected visual acuity (BCVA): this test is used to determine the smallest letters that can be read on a standardized chart. Un-corrected visual acuity (UCVA): the smallest letter that can be read unaided. Pinhole visual acuity (PHVA): the smallest letter that can be read without the interference of optical problems.

Slit lamp exam: a microscope is used to provide a magnified view of different parts of the eye and to determine inflammation (cell/flare) that is common with any ophthalmic surgery.

Visual acuity and slit lamp examinations are part of routine post-operative care. Pachymetry measurements are for research purposes to determine if there's less corneal swelling after cataract surgery in the lower IOP group.

The primary end point is: difference in CCT post-op at 4 hours between High vs Low IOP groups. Secondary endpoints include: CCT at POD#1 and POW#1, Cell/Flare at POHr4 and POD1, and inflammatory markers: levels of prostaglandin IL-6, IL-8, IL-1 β , TNF- α , PGE2, MCP-1. Aqueous samples will be sent with de-identified patient information and aqueous analysis will be performed by the University of California, Irvine Molecular Biology and Biochemistry Labs. The laboratory will be masked to which treatment the subject received and will only provide the aqueous analysis report for the study.

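### The primary endpoint is worded as CCT at 4 hours but tested as CCT change: state change from baseline in both places and adjust for baseline CCT

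*Combined protocol and SAP*

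**What the plan says.** The documents describe the primary outcome in three places.

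- Methods, endpoint paragraph: the primary endpoint is the "difference in CCT post-op at 4 hours between High vs Low IOP groups". Neither change nor baseline is mentioned.
- Analysis: "Difference in mean CCT change at 4 hrs post-surgery between high vs low IOP will be assessed using t-test with a P-value <0.05". The reference point for the change is not given and no covariate is named.
- Sample Size Justification: "the expected mean CCT change between the high vs low groups is hypothesized to be 32um, with a standard deviation of 40um".

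The post-operative procedures table schedules pachymetry at baseline, 4 hours, 20-24 hours and 1 week, so every patient should have a baseline CCT. The text under the table gives the reason for measuring it: "Pachymetry measurements are for research purposes to determine if there's less corneal swelling after cataract surgery in the lower IOP group". Swelling implies a comparison with the pre-operative cornea. For the rest, the Analysis section says: "Descriptive statistics will be used for the other secondary endpoints".

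**The concern.** The only sentence that defines the primary endpoint names one variable (CCT at 4 hours) and the only sentence that specifies its test names another (CCT change). The sample size and the purpose of pachymetry both point to change, but the definition does not say so. An analyst could defend either as prespecified. The documents describe masking for the post-operative examiner and the laboratory, but not for whoever analyses the data.

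This is not a question of bias. With random allocation, expected baseline CCT is the same in both arms, so level and change have the same expected between-group difference. They differ in variance, and so in power and in the p-value of any one trial. If the choice is made after seeing both results, the 5% error rate no longer holds.

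A second point follows. Baseline CCT is collected but enters the plan only through subtraction. Using it as a covariate makes the choice between level and change irrelevant and can add some precision.

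**Working it through.** **Inputs from the documents:** difference 32 µm, SD 40 µm, alpha 0.05, power 0.85, 56 evaluable eyes, 66 enrolled. I take 40 µm as the SD of change, as the sentence reads, and 28 eyes per arm.

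**Step 1: the plan's own figure.** n per arm = 2 × (1.960 + 1.036)² × 40² / 32² = 28.06, or 56.1 in total. This matches the stated 56 and shows that a two-sided test was meant; a one-sided test would need 22.5 per arm. Allowing 15% attrition, 56 / 0.85 = 65.9, which gives 66. With the noncentral t distribution at 28 per arm, the planned t-test on change has power 83.6%.

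**Step 2: assumptions.** The documents give neither the baseline SD (sb) nor the correlation r between baseline and change. I take sb = 33 µm (range 25 to 40) and r from 0 to -0.4.

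**Step 3: SD and power of each analysis.**

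- Level at 4 hours: SD = √(sb² + 40² + 2·r·sb·40), 54 df. For sb = 33 and r = 0: √(1089 + 1600) = 51.9.
- Change: SD = 40 at every r, 54 df.
- ANCOVA: residual SD = 40·√(1 − r²), 53 df.

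| r | Level SD (sb 33) | Power, level (sb 25 to 40) | Power, change | Power, ANCOVA, formula | Power, ANCOVA, simulated (sb 33) |
|---|---|---|---|---|---|
| 0 | 51.9 | 62% (70 to 55%) | 83.6% | 83.6% | 83.0% |
| -0.2 | 46.5 | 72% (79 to 64%) | 83.6% | 85.1% | 84.7% |
| -0.3 | 43.6 | 77% (83 to 70%) | 83.6% | 86.9% | 86.3% |
| -0.4 | 40.4 | 83% (88 to 77%) | 83.6% | 89.4% | 88.6% |

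The simulated column allows for chance baseline imbalance and an estimated slope. Against 83.6%, the ANCOVA gain is -0.6, +1.1, +2.7 and +5.0 points. Level and change have equal power where sb² + 2·r·sb·40 = 0, that is r = −sb/80: -0.31, -0.41 and -0.50 for sb = 25, 33 and 40.

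**Step 4: consequence of two wordings.** Simulation used 40,000 trials per setting, bivariate normal data and 28 per arm.

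- With a true 32 µm effect, exactly one of the level and change tests is significant in 12.4% (sb 25, r = -0.4) to 33.1% (sb 40, r = 0) of trials.
- With no effect, at least one of the two has p < 0.05 in 7.6% to 9.0% of trials. Each test alone, and ANCOVA, stay at 4.8% to 5.3%. Simulation error on an 8% figure is √(0.08 × 0.92 / 40,000) = 0.14 points (one standard error).

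**Step 5: why ANCOVA removes the ambiguity.** The 4-hour value equals baseline plus change. With baseline in the model, switching the outcome from change to level raises the baseline slope by exactly 1. The arm coefficient, residuals, standard error and p-value do not change.

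**Step 6: a second set of assumptions.** Suppose instead that baseline and 4-hour CCT have equal SDs and correlation ρ of 0.5 to 0.9. ANCOVA power is then 92.4% to 85.5% and level power 83.6% to 26.0%. At ρ = 0.9 this implies a CCT SD of 40/√(2 × 0.1) = 89.4 µm, so I rely on the more cautious figures in the table.

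**The case against.** The strongest reply is that the plan names only one primary test. The Analysis section labels it as the primary endpoint, it is on change, and the sample size agrees. The protocol also requires that it be followed as written, so testing the raw 4-hour value would depart from the Analysis section. On this view the 7.6% to 9.0% is what selective reporting could produce, not the error rate of the plan. That is correct, and I present it only as the size of the opening the wording leaves. It does not remove the opening, because the endpoint definition is also part of the protocol as written.

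The second reply is that aligning the wording closes the choice by itself, so ANCOVA must stand on precision alone, where the gain is nil to modest and slightly negative at r = 0. This is largely fair. The t-test on change is valid, and adjustment is an improvement, not a repair. It still merits a place because the covariate is already collected and any leftover ambiguity could no longer affect the result.

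Third, apart from the 83.6%, the comparative figures rest on an assumed baseline SD and r. The simulation also ignores the exclusion of corneas under 490 microns, which would narrow the baseline distribution. Both points stand. They affect the size of the figures, not the existence of the discrepancy or the algebra of Step 5.

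**Conclusion.** The concern holds. The primary endpoint is defined as a level and tested as a change, the reference point for the change is not stated, and an available baseline covariate is unused. The planned test is valid and the sample size reproduces, so this should be corrected but does not invalidate the design.

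The sizes above assume that 40 µm is the SD of change, 28 evaluable eyes per arm, and the stated ranges for baseline SD and r. The identity of the ANCOVA result under either coding needs none of those assumptions.

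**What to change.** Make these edits before any outcome data are examined by arm.

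- Methods and Analysis: name one primary endpoint, the change in CCT from baseline to 4 hours after surgery, compared between arms. This is the basis of the sample size.
- Analysis: make the primary analysis ANCOVA with arm and baseline CCT as the only terms, two-sided alpha 0.05, reporting the adjusted mean difference with its 95% CI. Keep the two-sample t-test on change as a sensitivity analysis.
- Sample Size Justification: say that 40 µm is the SD of the change. Keep N = 66.
- Secondary endpoints: leave them descriptive. CCT at day 1 and week 1 has the same wording gap, and the same edit can say whether level or change is summarised.

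The cost is a few sentences of protocol text and one degree of freedom, with no new visits, measurements or patients. Because the primary analysis changes, the protocol's own amendment rule probably calls for a written, IRB-approved amendment.

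### Minor, cheap improvement: the primary t-test uses only eyes with baseline and 4-hour CCT readings, although later scheduled readings could recover some eyes that miss the 4-hour visit

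*Combined protocol and SAP*

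**What the plan says.** The primary analysis is one sentence in the Analysis section: "Difference in mean CCT change at 4 hrs post-surgery between high vs low IOP will be assessed using t-test with a P-value <0.05". Whether the test is one- or two-sided is not stated.

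The Sample Size Justification assumes that "the expected mean CCT change between the high vs low groups is hypothesized to be 32um, with a standard deviation of 40um" and continues: "With a Type I/II error rate of alpha=0.05 and power=0.85, a sample size of 56 eyes are needed". It then adds eyes for loss: "additional 10 eyes to account for ~15 attrition; N=66". The figure 15 has no unit, but 10/66 = 15.2%, so a percentage is evidently meant.

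The Methods section schedules post-operative visits "at 4hrs (early post-op), POD#1 (20-24hrs), POW#1", and the procedures table shows pachymetry at baseline and at all three visits. The later readings enter only as secondary endpoints ("Secondary endpoints include: CCT at POD#1 and POW#1"), for which the Analysis section plans descriptive statistics.

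The documents name no analysis set, no rule for a missing 4-hour reading and no sensitivity analysis. They do not say when attrition is expected or whether lost eyes would be seen again.

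**The concern.** A t-test of change at 4 hours drops any eye without a 4-hour value, even if its baseline, day-1 and week-1 values are all present. The only provision for loss is enrolling more eyes. That protects power but does not protect the estimate: the difference among eyes with a 4-hour reading is unbiased only if missing the reading does not distort the comparison between arms. The later CCT readings are probably related to the 4-hour value and are collected anyway, yet the primary analysis makes no use of them.

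At stake are a small amount of power and some protection against bias, and only for eyes that miss 4 hours and then return. The point concerns missing 4-hour readings. It counts no gain from adjusting for baseline CCT.

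**Working it through.** **Inputs from the plan.** Difference 32 µm, SD 40 µm, alpha 0.05 (two-sided assumed), power 0.85, 56 evaluable eyes, 66 enrolled. Allocation is by random number ("Even will be high IOP; Odd will be low IOP"), so 33 per arm enrolled and 28 per arm evaluable hold in expectation.

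**Reproducing the plan's figures.**
- Normal approximation: n per arm = 2 × [40 × (1.960 + 1.036)/32]² = 28.06, or about 56 in total (58 if rounded up strictly in each arm). One-sided 0.05 gives 46, which does not match.
- Inflation: 56/0.85 = 65.9, so 66.
- Power at 28 per arm: 84.9% by the normal approximation and 83.6% by the noncentral t, which suits the planned test. The t-test needs 30 per arm for 85%.

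The stated 56 and 66 therefore reproduce, and the budgeted loss is already paid for to within about 1.4 points (85 − 83.6).

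**What later readings could recover.** Suppose 28 eyes per arm have a 4-hour value and n_seen have a day-1 value. With correlation ρ between the two, the effective number per arm for the 4-hour mean is

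n_eff = 1 / [(1 − ρ²)/28 + ρ²/n_seen].

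Example, ρ = 0.5 and all five missing eyes returning (n_seen = 33): 1/[0.75/28 + 0.25/33] = 1/(0.02679 + 0.00758) = 29.1.

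The documents give neither ρ nor the share returning, so both are assumed. Power is from the noncentral t:

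| Missing eyes seen later, per arm | ρ = 0.5 | ρ = 0.7 | ρ = 0.9 |
|---|---|---|---|
| All 5 (n_seen = 33) | n_eff 29.1, 85.1% | 30.3, 86.4% | 31.9, 88.2% |
| Half (n_seen = 30.5) | 28.6, 84.4% | 29.2, 85.2% | 30.0, 86.1% |
| 1 (n_seen = 29) | 28.2, 84.0% | 28.5, 84.3% | 28.8, 84.7% |
| None | 28, 83.6% | 28, 83.6% | 28, 83.6% |

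The best case gains 1.5 to 4.6 points. The formula ignores the small cost of estimating the covariance.

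**Bias under assumed missingness.** All scenarios simulate 33 eyes per arm and a true difference of 32 µm. They compare the difference among eyes with a 4-hour reading with an estimate that regresses the 4-hour value on day 1 within arm.

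1. *One-sided loss.* Five eyes per arm are missing: in the high-IOP arm mainly those with more day-1 swelling, in the low-IOP arm at random (day-1 SD 25, day-1 difference 12; 20,000 trials). At ρ = 0.3/0.5/0.7/0.9 the t-test difference is 29.7/28.3/26.6/25.1 µm. The day-1-based estimate is 32.0/32.0/31.9/31.9 µm.
2. *Loss tied to day-1 swelling in opposite directions by arm*, about 15% missing (day-1 SD 30, day-1 difference 16; 4,000 trials). At ρ = 0.5/0.7/0.9: 27.2/25.4/23.5 µm against 31.8/32.0/31.9 µm.
3. *Opposite directions, driven by the 4-hour swelling itself* (same means and SDs as 2). 18.3/18.4/18.5 µm against 21.3/24.5/29.2 µm, so the correction is only partial.
4. *Same direction in both arms* (same means and SDs as 2). The t-test difference is 31.9 to 32.2 µm: no material bias to correct.

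With loss completely at random under the settings of scenario 1, the SD of the estimate falls from 10.7 to 10.5 µm at ρ = 0.5 and from 10.7 to 10.0 µm at ρ = 0.9. The model then costs nothing material.

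**The case against.** The strongest reply is that four hours is the first post-operative visit, on the day of surgery. Eyes lost after it stay in the t-test, and eyes lost for good before it have no later reading for any model to use. Only eyes that skip the same-day visit and then return are recovered, and nothing shows that these make up the 15%. This stands. A reader might infer that the plan is set to discard 10 of 66 eyes with usable data; the documents give no visit or cause for the attrition and do not support that. It remains fair to read the allowance as loss to the 4-hour endpoint, since that is the endpoint it inflates. A missed reading is also not the same as dropout: "Pachymetry measurements are for research purposes to determine if there's less corneal swelling after cataract surgery in the lower IOP group", whereas acuity and slit-lamp examinations are routine care, so one reading could be missed in a patient who still attends.

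Second, some losses may come from exclusion criteria that can be known only during or after surgery. That is a question of who belongs in the analysis set, and a repeated-measures model does not answer it. This also stands.

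Third, a pre-specified t-test at a single time point is valid and matches the sample-size calculation, while the model makes the primary result depend on secondary readings and on an assumption that cannot be verified. The first part is correct, and a reader should not infer that the t-test is wrong. The second is the real price of the change. Completers-only analysis, however, also rests on an unverifiable assumption about missingness, and the day-1-based estimate was no worse in any way that mattered.

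**Conclusion.** The point holds as a minor, low-cost improvement. The t-test is not invalid, and the plan's sample size already covers the budgeted loss approximately.

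The possible gain runs from nothing, if no missing eye returns, to power of about 85-88% against 83.6% if all five per arm return. These figures assume 28 of 33 eyes per arm with a 4-hour value and a correlation of 0.5-0.9, neither of which the documents establish.

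A reader might take the simulated shortfalls of several µm as the expected bias. They are not: they come from chosen patterns in which loss differs between arms, and no text in the plan points to such a pattern. The model corrects fully only when the observed CCT readings explain who is missing, and only partly when missingness depends on the unseen 4-hour value. When loss is alike in both arms there is no material bias to correct.

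**What to change.** In the Analysis section, before any unmasked data are seen, pre-specify:

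- **Primary analysis:** a repeated-measures model of CCT at baseline, 4 hours, 20-24 hours and 1 week in all randomised eyes with any reading, with a common baseline mean for the arms, arm-by-visit effects, unstructured covariance and Kenward-Roger degrees of freedom.
- **Primary result:** the low-minus-high contrast at 4 hours, two-sided 0.05.
- **Sensitivity analysis:** the planned t-test on eyes with a 4-hour reading.

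The same text would supply the missing analysis set and the rule for a missing 4-hour reading. It should also say how eyes meeting the intra- or post-operative exclusion criteria are handled, because the model does not settle that.

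The cost is a few sentences and slightly more programming, with no new visit or measurement. The downside is a missing-at-random assumption, and there is no benefit for eyes lost at every visit.
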